4.5.11 Chest X-Rays

Patients with a positive PPD test (without a history of BCG vaccination) or a QFT-G that is positive or indeterminate will require a chest X-ray to review for evidence of active TB, including posteroanterior and lateral views, unless a chest X-ray has been performed within 3 months prior to screening and the report is available for review. A chest computed tomography scan may be substituted for a chest X-ray. Chest X-rays should only be performed if patients first meet all other study eligibility criteria.

All imaging should be read by a radiologist or per local requirements.

4.5.12 Asthma Exacerbations

At each study visit, the investigator will ask directed questions to assess whether the patient experienced any asthma exacerbations as defined in Section 2.1.1 since the last study visit.

Given that asthma exacerbations comprise part of the primary endpoint in this study, a dedicated eCRF will be used to record information regarding asthma exacerbation events. An asthma exacerbation must also be reported as an adverse event (or serious adverse event, as applicable) (refer to Section 5.3.5.10 for more details). Sites should record all medications used for treatment of the asthma exacerbation in the appropriate eCRF.

Patients who experience symptoms consistent with an asthma exacerbation should be asked to come to the clinic for an unscheduled visit if possible. Additional evaluations will be performed as outlined in the schedule of activities (see [Appendix 1](#)).

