3.1.3 Internal Monitoring Committee

Periodic safety reviews will be performed by the Sponsor's Internal Monitoring Committee (IMC) as outlined in the IMC Charter. This committee will be unblinded to treatment assignments and will include a clinical scientist, drug safety scientist, biostatistician, and statistical programmer from the Sponsor. The IMC members will not have direct contact with investigational staff or site monitors. The IMC may decide to unblind the study team to enable decision-making. The IMC may invite representatives from other functional areas on an ad-hoc basis when additional expertise is required (e.g., clinical pharmacology, research) or invite additional Sponsor scientists to participate in data analyses and review.

The IMC will meet at a frequency dictated by the IMC charter but no less frequently than once every 3 months. Additionally, ad-hoc IMC meetings may be convened immediately or expeditiously at any time to address potential safety concerns if periodic review of blinded safety data indicates 3 or more patients with serious or Grade 3 or higher adverse events (excluding asthma exacerbations) that the investigator or Sponsor determines to be related to study treatment, within the same MedDRA high level term.

The IMC will assess the severity, relatedness, and reversibility of adverse events, the degree of imbalance between treatment arms, the similarity and frequency of events under a single higher level term, the plausibility of a common mechanism, possible risk mitigation measures, and may recommend changes to study conduct (including termination of study) as appropriate.

At any time during the study, the Sponsor may choose to inactivate and suspend enrollment and further dosing or reduce the dose due to safety concerns as recommended by the IMC. Should an ad-hoc IMC meeting be convened, enrollment of patients may be temporarily halted if warranted by the frequency and severity of the blinded adverse events, until the IMC evaluates the unblinded data and decides whether resumption of dosing is safe to proceed, or until IMC-recommended changes to the conduct of the study are implemented.

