4.6 TREATMENT, PATIENT, STUDY, AND SITE DISCONTINUATION

4.6.1 Study Treatment Discontinuation

Patients must permanently discontinue study treatment if they experience any of the following:

- Any medical condition that the investigator or Sponsor determines may jeopardize the patient's safety if he or she continues to receive study treatment
- Any Grade 4 adverse event that the investigator or Sponsor determines to be related to study treatment. This excludes asthma exacerbations, unless they meet one of the other criteria for study treatment discontinuation.

- Investigator or Sponsor determination that treatment discontinuation is in the best interest of the patient
- Pregnancy
- Suspicion of hypersensitivity or anaphylactic reaction to study drug (i.e., generalized urticaria or angioedema [WHO Grade 3 allergic reaction] or anaphylaxis [Grade 4 allergic reaction] related to study drug, or Grade 3 or 4 infusion related reaction)

The primary reason for study treatment discontinuation should be documented on the appropriate eCRF. Patients who discontinue study treatment prematurely will not be replaced and should continue follow-up for all other study procedures and measurements through the end of the study (Week 58).

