5.3.5.10 Worsening of Asthma

Medical occurrences or symptoms of deterioration that are anticipated as part of asthma should be recorded as an adverse event if judged by the investigator to have unexpectedly worsened in severity or frequency or changed in nature at any time during the study (e.g., an asthma exacerbation). When recording an unanticipated worsening of asthma on the Adverse Event eCRF, it is important to convey the concept that the condition has changed by including applicable descriptors (e.g., "asthma exacerbation").

Asthma exacerbation is defined as an acute worsening of asthma that requires a burst of systemic corticosteroids (refer to Section 2.1.1).

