6.5 SAFETY ANALYSES

The safety analysis population will consist of all randomized patients who received at least one dose of study drug during the 48-week double-blind treatment period, with patients grouped according to treatment received (MTPS9579A or placebo). Safety analysis of run-in patients will consist of all patients who received the single-blind placebo dose during the run-in period, regardless of whether or not the patient is randomly allocated into the double-blind treatment period. For this safety analysis, only events that occur during the 2-week run-in period will be included and grouped together since all patients will have received placebo.

Safety will be assessed through summaries of adverse events, laboratory test results, ECG parameters, physical examination findings, and vital signs. Verbatim descriptions of treatment-emergent adverse events will be coded using the MedDRA thesaurus terms and their severity by WHO Toxicity Grading Scale (see [Appendix 7](#)), and their incidence will be summarized by treatment arm. A treatment-emergent adverse event is defined as any new adverse event reported or worsening of an existing condition on or after the first dose of study drug during the 48-week double-blind treatment period. In addition, separate summaries will be generated for serious adverse events, adverse events of special interest, deaths, pregnancies, malignancies, anaphylaxis events, adverse events leading to discontinuation from the study, and adverse events leading to discontinuation of study drug.

Clinical laboratory data (serum chemistry, hematology evaluations, and urinalysis values) and vital signs will be summarized by descriptive statistics for each treatment group.

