## Output 4.4 Overview of Deaths and Adverse Events (AET01)

Protocol: GB41149

Analysis Population:

- (1) Placebo Run-in Period; Run-in safety-evaluable population (PERIOD1\_PEFL)
- (2) 48-Week Double-Blind Treatment Period and 12-Week Safety Follow-up Period; Safety-evaluable population (PERIOD2\_SE)

	Placebo (N = XXX)	MTPS9579A Active (N = XXX)	All Patients (N = XXX)
Total number of patients with at least one AE	nn (xx.x%)	nn (xx.x%)	nn (xx.x%)
Total number of AEs	nn	nn	nn
Total number of deaths	nn (xx.x%)	nn (xx.x%)	nn (xx.x%)
Total number of patients withdrawn from study due to an AE	nn (xx.x%)	nn (xx.x%)	nn (xx.x%)

Total number of patients with at least one			
AE with fatal outcome	nn (xx.x%)	nn (xx.x%)	nn (xx.x%)
Serious AE	nn (xx.x%)	nn (xx.x%)	nn (xx.x%)
Serious AE leading to withdrawal from treatment	nn (xx.x%)	nn (xx.x%)	nn (xx.x%)
Serious AE leading to dose modification/interruption	nn (xx.x%)	nn (xx.x%)	nn (xx.x%)
Related Serious AE	nn (xx.x%)	nn (xx.x%)	nn (xx.x%)
AE leading to withdrawal from treatment	nn (xx.x%)	nn (xx.x%)	nn (xx.x%)
AE leading to dose modification/interruption	nn (xx.x%)	nn (xx.x%)	nn (xx.x%)
Related AE	nn (xx.x%)	nn (xx.x%)	nn (xx.x%)
Related AE leading to withdrawal from treatment	nn (xx.x%)	nn (xx.x%)	nn (xx.x%)
Related AE leading to dose modification/interruption	nn (xx.x%)	nn (xx.x%)	nn (xx.x%)
Grade 3-5 AE	nn (xx.x%)	nn (xx.x%)	nn (xx.x%)

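### The headline AE, SAE and Grade 3+ patient totals pool asthma exacerbations (part of the primary endpoint) with all other events, and no planned summary gives the totals without them

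*Protocol*

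**What the plan says.** **Recording.** Protocol Section 4.5.12 gives exacerbations their own form because of their role in efficacy: "Given that asthma exacerbations comprise part of the primary endpoint in this study, a dedicated eCRF will be used". It then requires a second record: "An asthma exacerbation must also be reported as an adverse event (or serious adverse event, as applicable". It refers sites to Section 5.3.5.10 for detail, where the wording is conditional. Anticipated asthma deterioration "should be recorded as an adverse event if judged by the investigator to have unexpectedly worsened in severity or frequency", with an exacerbation given as the example and a cross-reference to Section 2.1.1.

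**Where exacerbations are set apart.** The ad-hoc trigger of the Internal Monitoring Committee (Section 3.1.3) is "3 or more patients with serious or Grade 3 or higher adverse events (excluding asthma exacerbations") judged related and falling within one MedDRA high level term. The rule on related Grade 4 events in Section 4.6.1 adds: "This excludes asthma exacerbations, unless they meet one of the other criteria for study treatment discontinuation".

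**Where they are not.** Protocol Section 6.5 plans incidence of all treatment-emergent events by arm, and "separate summaries will be generated for serious adverse events, adverse events of special interest, deaths" and other categories, with no exclusion of exacerbations. SAP Output 4.4 opens with "Total number of patients with at least one AE" and has further rows for serious and for Grade 3 to 5 events. Outputs 4.7 and 4.10 carry a pooled patient total above the system organ class and preferred-term rows.

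**The concern.** Entry requires at least two exacerbations in the previous 12 months, so these events will be common in both arms. Any that lead to inpatient admission are SAEs under Sections 5.2.2 and 5.3.5.11. The headline safety rows therefore mix an outcome the drug is meant to reduce with events it might cause. If the drug works, fewer exacerbations on active treatment pull the total down and can offset a rise in other events. If it does not work, similar exacerbation rates in both arms shrink the contrast. Either way, a reader comparing arms on the top rows cannot tell whether similar totals mean similar harm. The protocol sets exacerbations apart in two of its safety rules, and the SAP does not carry that separation into its tables.

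**Working it through.** The plan attaches no rate, test or power figure to safety, so there is no stated result to reproduce. The denominators in SAP Output 1.1 are consistent: 65 + 69 = 134 safety-evaluable; 65/66 = 98.5%; 134/135 = 99.3%.

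**1. Can the pooled rows cancel?** Per arm, assuming the two kinds of event are independent, pooled risk = 1 − (1 − p_exac)(1 − p_other). All rates are assumed and shown as placebo vs active.

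| Row | Exacerbation | Other | Pooled |
|---|---|---|---|
| SAE | 6% vs 2% | 3% vs 7% | 8.8% vs 8.9% |
| SAE | 10% vs 4% | 3% vs 9% | 12.7% vs 12.6% |
| Grade 3+ | 15% vs 8% | 5% vs 12% | 19.2% vs 19.0% |
| Any AE | 45% vs 30% | 50% vs 60% | 72.5% vs 72.0% |

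Second line in full: 1 − 0.90 × 0.97 = 0.127 and 1 − 0.96 × 0.91 = 0.126, although the risk ratio for other SAEs is 9/3 = 3.0. With no exacerbation benefit (10% in both arms), the same line gives 12.7% vs 1 − 0.90 × 0.91 = 18.1%. The 6-point excess then shows as 5.4 points, so it is diluted but visible. These rates were chosen to cancel. They show that cancellation is possible, not how likely it is.

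**2. Counts at the actual arm sizes (assumed, no patient in both groups).** Serious exacerbations in 7/65 vs 3/69 and other SAEs in 2/65 vs 6/69:
- pooled: 9/65 (13.8%) vs 9/69 (13.0%)
- excluding exacerbations: 2/65 (3.1%) vs 6/69 (8.7%)

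**3. Can the count be recovered by subtraction?** Let T be patients with any SAE and E patients with a serious exacerbation. The number with a non-exacerbation SAE lies between T − E and T, because a patient can have both. From the pooled row and the exacerbation count in step 2, that is 2 to 9 on placebo and 6 to 9 on active, and the ranges overlap. The other preferred-term rows can lower the upper limit to their sum. That meets T − E only when no patient appears in more than one row.

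**4. Is the asthma row the exacerbation set?** Not necessarily. Section 5.3.5.1 has events within 24 hours of dosing recorded as separate signs and symptoms, so an exacerbation then could appear as dyspnea. Conversely, Section 5.3.5.10 allows other unexpected asthma worsening to be recorded as an AE.

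**5. How much depends on grading?** Assume a 48-week exacerbation risk of 35% on placebo and a hazard ratio of 0.6, so active risk = 1 − 0.65^0.6 = 22.8%. Assume other Grade 3+ events in 8% vs 20%. Let s be the share of patients with an exacerbation whose event reaches Grade 3.

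| s | Exacerbation at Grade 3+ | Pooled Grade 3+ row |
|---|---|---|
| 30% | 10.5% vs 6.8% | 17.7% vs 25.5% |
| 50% | 17.5% vs 11.4% | 24.1% vs 29.1% |
| 100% | 35.0% vs 22.8% | 40.2% vs 38.2% |

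Only the last line reverses the direction.

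**The case against.** The strongest reply is that nothing is concealed. Outputs 4.7(4) and 4.10 are by system organ class and preferred term, with a patient total in each class, so exacerbations coded to one class leave the totals of the others untouched. Output 4.13 is by preferred term, and Output 4.15 covers events of special interest. Output 4.4 has related-event rows, and 4.11 and 4.12 tabulate related events. Table 4 of the protocol treats an event explained by underlying disease as unrelated, so those rows should drop many exacerbations. Outputs 4.32 and 4.33 list AEs and SAEs by patient, and 134 patients can be counted by hand. Safety is descriptive, and the committee's ad-hoc trigger already leaves exacerbations out.

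Most of this stands, and it confines the point to the headline rows. A reader might infer that the SAP hides non-asthma harm; the documents do not support that. What remains is that the related-event rows also drop non-asthma events judged unrelated, and a hand count would be unplanned and made on unblinded data. With 65 and 69 patients, an excess scattered over single-patient terms is hard to add up by eye.

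Two other strong readings also fail. A reader might take every exacerbation as Grade 3 or higher from the severity wording in Table 3. That table applies only to events absent from the WHO scale, and Appendix 7 lists acute bronchospasm, with a Grade 2 level for treated episodes that normalize with a bronchodilator. A reader might also take Section 5.3.5.10 as a competing definition without the 3-day or emergency-visit conditions. It cites Section 2.1.1, which contains them, and names an exacerbation as its example. What is left is a mismatch between an obligation and a conditional.

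**Conclusion.** The point holds as a reporting gap. Exacerbations must be AEs or SAEs, the top patient-level rows pool them with everything else, and no planned summary gives patients with at least one non-exacerbation AE, SAE or Grade 3+ AE. In those rows a benefit can offset, and background events can dilute, an excess of other events.

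The size cannot be stated. The documents give no rates of serious or Grade 3+ exacerbations or of other such events. The near-exact cancellations rest on chosen rates and on independence. The apparent reversal of a 2.5-fold excess (8% vs 20%) needs all exacerbations to reach Grade 3 and should not be relied on; at 30% the excess is plain.

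Separate rows would not amount to a powered safety test either. For the SAE and Grade 3+ lines in step 1, power for other events alone is 0.18 to 0.30 at a two-sided 0.05 level, which is itself an assumption because the plan sets no safety test. The gain is a clearer description. Efficacy results are not affected.

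**What to change.** In SAP Outputs 4.4, 4.7(2), 4.7(4) and 4.10, keep the all-event totals and add totals that exclude asthma exacerbations. Identify the excluded events by linking the AE record to the dedicated exacerbation eCRF, not by preferred term. Report both sets side by side whenever the arms are compared.

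In the protocol, reconcile Section 5.3.5.10 with 4.5.12 so that every event meeting Section 2.1.1 is recorded as an AE and the excluded set is well defined.

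The cost is one analysis flag, a few extra table rows and about one sentence of protocol text.

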4.5.13 Blood Samples for Whole Genome Sequencing (Patients at Participating Sites)

At participating sites, blood samples will be collected for DNA extraction to enable WGS to identify variants that are predictive of response to study drug, are associated with progression to a more severe disease state, are associated with susceptibility to developing adverse events, can lead to improved adverse event monitoring or investigation, or can increase the knowledge and understanding of disease biology and drug safety. Research will be aimed at exploring inherited characteristics. The samples may be sent to one or more laboratories for analysis.

Collection and submission of blood samples for WGS is contingent upon the review and approval of the exploratory research by each site's Institutional Review Board or Ethics Committee (IRB/EC) and, if applicable, an appropriate regulatory body. If a site has not been granted approval for WGS, this section of the protocol (Section 4.5.13) will not be applicable at that site.

Genomics is increasingly informing researcher's understanding of disease pathobiology. WGS provides a comprehensive characterization of the genome and, along with clinical data collected in this study, may increase the opportunity for developing new therapeutic approaches or new methods for monitoring efficacy and safety or predicting which patients are more likely to respond to a drug or develop adverse events. Data will be analyzed in the context of this study but will also be explored in aggregate with data from other studies. The availability of a larger dataset will assist in identification and characterization of important biomarkers and pathways to support future drug development.

For sampling procedures, storage conditions, and shipment instructions, see the laboratory manual.

Blood samples collected for WGS are to be stored until they are no longer needed or until they are exhausted. However, the storage period will be in accordance with the IRB/EC-approved Informed Consent Form and applicable laws (e.g., health authority requirements).

Refer to Section 4.5.9 for details on use of samples after patient withdrawal, confidentiality standards for data, and availability of data from biomarker analyses.

4.5.14 Optional Methacholine Challenge Test

Consenting patients who meet additional inclusion criteria (Section 4.1.1.3) will undergo an optional methacholine challenge test, which should be performed before study drug dosing and within the visit windows for randomization and the Week 30 visit.

Methacholine challenge will be performed using standard techniques (Coates et al. 2017) and as described in the study PFT manual.

The Informed Consent Form will contain a separate section that addresses this optional test. A separate, specific signature will be required to document a patient's agreement to undergo optional testing. The investigator should document whether the patient has given consent to participate and (if applicable) the date(s) of consent, by completing the Optional Methacholine Challenge Test Informed Consent eCRF.

4.5.15 Optional Samples for Research Biosample Repository

4.5.15.1 Overview of the Research Biosample Repository

The Research Biosample Repository (RBR) is a centrally administered group of facilities used for the long-term storage of human biological specimens, including body fluids,

solid tissues, and derivatives thereof (e.g., DNA, RNA, proteins, peptides). The collection, storage, and analysis of RBR samples will facilitate the rational design of new pharmaceutical agents and the development of diagnostic tests, which may allow for individualized drug therapy for patients in the future.

Samples for the RBR will be collected from patients who give specific consent to participate in this optional research. RBR samples will be analyzed to achieve one or more of the following objectives:

- To study the association of biomarkers with efficacy or disease progression
- To identify safety biomarkers that are associated with susceptibility to developing adverse events or can lead to improved adverse event monitoring or investigation
- To increase knowledge and understanding of disease biology and drug safety
- To study drug response, including drug effects and the processes of drug absorption and disposition
- To develop biomarker or diagnostic assays and establish the performance characteristics of these assays

4.5.15.2 Approval by the Institutional Review Board or Ethics Committee

Collection, storage, and analysis of RBR samples is contingent upon the review and approval of the exploratory research and the RBR portion of the Informed Consent Form by each site's IRB/EC and, if applicable, an appropriate regulatory body. If a site has not been granted approval for RBR sampling, this section of the protocol (Section 4.5.15) will not be applicable at that site.

4.5.15.3 Sample Collection

The following samples will be stored in the RBR and used for research purposes, including, but not limited to, research on biomarkers related to MTPS9579A, diseases, or drug safety:

- Leftover blood, serum, nasal mucosal lining fluid, and urine samples and any derivatives thereof (e.g., DNA, RNA, proteins, peptides)

The above samples may be sent to one or more laboratories for analysis of germline or somatic variants via WGS or other genomic analysis methods. Genomics is increasingly informing researcher's understanding of disease pathobiology. WGS provides a comprehensive characterization of the genome and exome, respectively, and, along with clinical data collected in this study, may increase the opportunity for developing new therapeutic approaches or new methods for monitoring efficacy and safety or predicting which patients are more likely to respond to a drug or develop adverse events.

Data generated from RBR samples will be analyzed in the context of this study but may also be explored in aggregate with data from other studies. The availability of a larger

dataset will assist in identification and characterization of important biomarkers and pathways to support future drug development.

For sampling procedures, storage conditions, and shipment instructions, see the laboratory manual.

RBR samples are to be stored until they are no longer needed or until they are exhausted. However, the RBR storage period will be in accordance with the IRB/EC–approved Informed Consent Form and applicable laws (e.g., health authority requirements).

